9.7.1.8.1 EXTENT OF EXPOSURE

The extent of exposure to study drug will be summarized as cumulative extent of exposure in 3-month intervals. The number and percent of subjects will be presented by treatment group. Duration of exposure will be summarized using descriptive statistics in 3-month intervals. The number and percent of subjects will be presented by treatment group.

9.7.1.8.2 ADVERSE EVENTS

The AE verbatim descriptions (investigator terms from the eCRF) will be classified into standardized medical terminology using the Medical Dictionary for Regulatory Activities (MedDRA). Adverse events will be coded to the MedDRA (Version 17.0 or higher) lower level term closest to the verbatim term. The linked MedDRA preferred term and primary system organ class (SOC) are also captured in the database.

A TEAE is defined as an AE that emerges during treatment, having been absent at pretreatment (Baseline) or

- Reemerges during treatment, having been present at pretreatment (Baseline) but stopped before treatment, or
- Worsens in severity during treatment relative to the pretreatment state, when the AE is continuous.

Only those AEs that are treatment-emergent will be included in summary tables. All AEs, treatment-emergent or otherwise, will be presented in subject data listings.

The TEAEs will be summarized by treatment group on the Safety Analysis Set. The incidence of TEAEs will be reported as the number (percentage) of subjects with TEAEs by SOC and preferred term. A subject will be counted only once within an SOC and preferred term, even if the subject experienced more than 1 TEAE within a specific SOC and preferred term. The number (percentage) of subjects with TEAEs will also be summarized by maximum severity (mild, moderate, or severe). The number (percentage) of subjects with TEAEs will also be summarized by relationship to study drug (Yes [related] and No [not related]).

The number (percentage) of subjects with treatment-related TEAEs will be summarized by SOC and preferred term. Treatment-related TEAEs include those events considered by the investigator to be related to study drug. The number (percentage) of subjects with treatment-related TEAEs will also be summarized by maximum severity (mild, moderate, or severe).

Adverse events will be summarized by the following subgroups: *ApoE4* status (positive or negative), prior treatment with AChEIs or memantine (no or yes), and clinical population (MCI/Prodromal or mild to moderate AD). (revised per Amendment 01)

The number (percentage) of subjects with TEAEs leading to death will be summarized by MedDRA SOC and preferred term for each treatment group. A subject data listing of all AEs leading to death will be provided.

The number (percentage) of subjects with treatment-emergent SAEs will be summarized by MedDRA SOC and preferred term for each treatment group. A subject data listing of all SAEs will be provided.

The number (percentage) of subjects with TEAEs leading to discontinuation from study drug will be summarized by MedDRA SOC and preferred term for each treatment group. A subject data listing of all AEs leading to discontinuation from study drug will be provided.

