In the MAD study, AEs of interest included relapse of orolabial herpes, viral respiratory tract infection, drug rash, and abnormal dreams. More details are available in the Investigator's Brochure. In summary, E2609 administered at doses of 200 and 400 mg was associated with reductions in CD4 (T helper cells), CD8 (cytotoxic T cells), and CD19 (B cells) counts at Day 8. These reductions were more clearly evident by Day 15, consistent with a treatment by time interaction in the statistical analysis. There was evidence that the lower doses of 50 to 100 mg also caused some reduction in CD4 lymphocyte counts by Day 15. Doses above 100 mg appeared to be associated with greater reductions in CD4 and CD8 lymphocyte counts, which occurred earlier in the treatment period compared with the effects of 25 to 100 mg doses. These effects on lymphocyte counts gradually resolved from Day 20 to Day 35, which were 6 and 21 days, respectively, after administration of the last dose of E2609 on Day 14. Reductions in CD4 and CD8 lymphocyte counts at doses of 200 and 400 mg to a level close to or less than the lower limit of normal (LLN) could be associated with increased risk of developing relapse of orolabial herpes or other infections.

In Study 003, a drug-drug interaction study, PK results showed that itraconazole (a potent inhibitor of cytochrome P450 [CYP3A4] and carboxyesterase-2 [CES2]) increased by approximately 70% the area under the concentration \times time curve (AUC) of E2609. Consequently, strong inhibitors of CYP3A4 will be prohibited in this study.

Rifampin (a potent CYP3A4 inducer) caused a mild decrease (by approximately 20%) of the AUC of E2609. Therefore, no restrictions are required for the use of concomitant medications which are known to be inducers of CYP450 enzymes. Donepezil (a moderate CES2 inhibitor) caused a mild increase (by approximately 20%) of the AUC of E2609 when coadministered with E2609 but not when dosed at least 2 hours apart from E2609. E2609 (which inhibits the P-glycoprotein 1 transporter) did not affect the PK properties of digoxin. Nonclinical studies also indicated that other CYP pathways apart from CYP3A4 would not be major pathways of metabolism of E2609. Therefore, on the basis of drug interaction considerations, the only restriction of concomitant medications is that for strong inhibitors of CYP3A4.

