9.1.2 Randomization Phase

Subjects who complete the Baseline Visit assessments, and are eligible based on the inclusion and exclusion criteria (see [Section 9.3.1](#) and [Section 9.3.2](#)), will begin the Randomization Phase no more than 10 days after completion of the Baseline Visit assessments and confirmation of the eligibility of the subject based on the results of all the Baseline Visit assessments (revised per Amendment 02).

The Randomization Phase will consist of a Treatment Period of 78 weeks duration and a Follow-Up Period of 12 weeks after the last dose of study drug.

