9.5.1.5.1 ADVERSE EVENTS AND EVENTS ASSOCIATED WITH SPECIAL SITUATIONS

An AE is any untoward medical occurrence in a subject or clinical investigation subject administered an investigational product. An AE does not necessarily have a causal relationship with the medicinal product. For this study, the study drug is E2609.

The criteria for identifying AEs in this study are:

- Any unfavorable and unintended sign (including an abnormal laboratory finding), symptom, or disease temporally associated with the use of an investigational product, whether or not considered related to the investigational product (Note: It is not necessary to report every sign or symptom as a separate AE if the overall disease [diagnosis] is being reported as an AE.)
- Any new disease or exacerbation of an existing disease
- Any deterioration in nonprotocol-required measurements of a laboratory value or other clinical test (eg, ECG or x-ray) that results in symptoms, a change in treatment, or discontinuation of study drug
- Recurrence of an intermittent medical condition (eg, headache) not present pretreatment (Baseline)
- An abnormal laboratory test result should be considered an AE if the identified laboratory abnormality leads to any type of intervention, discontinuation of study drug, or withholding of study drug, whether prescribed in the protocol or not

All AEs observed during the study will be reported on the eCRF. All AEs, regardless of relationship to study drug or procedure, should be collected beginning from the time the subject signs the study ICF through the last visit (Visit 20, as shown in [Table 7](#)). For subjects who discontinue early from study drug but undertake further efficacy assessments, AEs will only be collected for 3 months after the last dose of study drug, ie, through to the final follow-up visit (Visit 20). Subjects who fail screening primarily due to AE(s) must have the AE(s) leading to screen failure reported on the Screening Disposition eCRF. SAEs will be collected for 3 months after the last dose of study drug, ie, through to the final Follow-Up visit (Visit 20). For subjects who discontinue early from study drug but continue with further efficacy assessments, SAEs will be solicited only for 3 months after the last dose of study drug (ie, up to the final follow up visit [Visit 20]). However, any SAEs volunteered by subjects after this time point must be reported according to standard procedures. (revised per Amendment 04)

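### Adverse events that begin after the last dose are collected for 12 weeks but enter no by-arm adverse-event table

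*Protocol*

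**What the plan says.** Section 9.7.1.8.2 defines the treatment-emergent adverse event (TEAE): "A TEAE is defined as an AE that emerges during treatment, having been absent at pretreatment (Baseline"). Two further limbs cover events that come back and events that get worse, and both are also confined to the time during treatment. The section continues: "Only those AEs that are treatment-emergent will be included in summary tables". The remaining events are left to listings: "All AEs, treatment-emergent or otherwise, will be presented in subject data listings". The tables for deaths and serious events in the same section are likewise limited to treatment-emergent events.

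Section 9.1.2 treats dosing and follow-up as two periods: "The Randomization Phase will consist of a Treatment Period of 78 weeks duration and a Follow-Up Period of 12 weeks after the last dose".

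Collection runs past the last dose. Section 9.5.1.5.1 says that AEs are "collected beginning from the time the subject signs the study ICF through the last visit (Visit 20"), and that for subjects who stop drug early but stay for efficacy visits "AEs will only be collected for 3 months after the last dose of study drug". Section 9.5.4.1 sets the same three months for SAEs. Section 9.1.2.3 schedules four follow-up visits, 2, 4, 8 and 12 weeks after the last dose.

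Section 7.1 gives the only recovery data. In the 14-day multiple-dose study the lymphocyte effects "gradually resolved from Day 20 to Day 35, which were 6 and 21 days, respectively, after administration of the last dose".

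**The concern.** The trial asks about adverse events for 12 weeks after dosing and then bars those with onset in that period from every AE incidence table. A listing shows that an event happened. It does not give the number and percentage of subjects by arm, which is what a reader compares.

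The second primary objective in Section 8.1 is safety, with immunological and hematological parameters named. Section 7.1 links CD4 and CD8 counts near or below the lower limit of normal, seen at 200 and 400 mg, to a possible increase in infection risk, and shows that the effects outlast dosing by days to weeks. An infection that begins two weeks after a subject finishes or permanently stops drug is therefore of interest, and the tables as specified would not count it.

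The gap is widest if futility is declared. Under Section 9.7.3 all treatment then stops and every subject is monitored for safety for three months. No AE with onset in those months would be tabulated.

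**Working it through.** **Inputs**

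- TEAE rule and table rule: Section 9.7.1.8.2.
- Treatment 78 weeks, follow-up 12 weeks: Section 9.1.2.
- Visit 18 at Day 547 and Visit 20 at Day 631: Table 7.
- Last dose on Day 14, resolution from Day 20 to Day 35: Section 7.1.
- Laboratory summaries: Section 9.7.1.8.3.

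**1. The plan's own recovery figures.** 20 − 14 = 6 days and 35 − 14 = 21 days. Both agree with the stated figures.

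**2. Length of follow-up.** 631 − 547 = 84 days, and 84 / 7 = 12 weeks. This agrees with the stated length.

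**3. Share of follow-up covered by documented recovery.** 21 / 84 = 25%. This comes from 14 days of dosing. The protocol gives no figure for recovery after 78 weeks.

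**4. Share of post-randomization AE collection that is not tabulated.**

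- Completer: 12 / (78 + 12) = 12 / 90 = 13%.
- Stop at Week 12 (illustrative): 12 / (12 + 12) = 12 / 24 = 50%.
- Stop at Week 4 (illustrative): 12 / (4 + 12) = 12 / 16 = 75%.

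The two stopping times are chosen to show the range. All three shares are calendar time and not event counts.

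**5. What happens to a finding that first appears at the Week 2 follow-up visit**

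| Finding | Treatment under the protocol |
|---|---|
| Low lymphocyte subset count | Tabulated by arm; Section 9.7.1.8.3 summarizes each postbaseline visit |
| Markedly abnormal laboratory value | Counted; the definition needs only a postbaseline value |
| Infection, new onset | Listing only |
| SAE, new onset | Listing only |
| Death from an AE that began on treatment | In the table; the rule turns on when the AE emerges or worsens |
| Death from an AE that began after the last dose | Listing only |

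The count and the infection that might accompany it are handled differently although they come from the same visit.

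**The case against.** **During treatment is not given in days.** Where the protocol wants a last-dose cutoff it says so, as for concomitant medication in Section 9.7.1.5, and an operational window is often set in the SAP. This stands in part, because a SAP could set one. However, Section 9.1.2 separates the Treatment Period from the Follow-Up Period, and the table rule is exclusive. A SAP that tabulated follow-up events would depart from the natural reading of the protocol.

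**The safety tables as a whole are not affected.** A reader might infer that follow-up events drop out of every safety table, or are lost. The documents do not support that. Laboratory values, lymphocyte subsets and immunoglobulins are summarized by visit, as are ECG and vital-sign statistics, and all AEs and SAEs are listed. The gap is in the AE incidence tables.

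**Events that cause discontinuation are captured.** This stands. An infection that leads to stopping drug began on treatment and is a TEAE. Under Section 9.3.3, confirmed low counts without infection lead first to temporary suspension, and nothing in Section 9.7.1.8.2 excludes an event during a suspension within the Treatment Period. The gap concerns new or worsening events after completion or permanent discontinuation.

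**No dose-related bias is shown.** A reader might infer that the untabulated events gather in the higher-dose arms, so that the tables understate the drug effect. That is possible, since some stopping rules rest on counts, infection and rash, and Section 7.1 reports some CD4 reduction at 50 to 100 mg. But the clearest reductions were at 200 and 400 mg, and Section 9.4.4 reports no infection or drug rash on 100 mg or less. No excess of post-dose infection at the trial's doses is documented.

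**A TEAE window through Visit 20 may dilute a contrast.** Documented recovery ends at day 21, so a single pooled window would add 84 − 21 = 63 days, or 9 weeks, of mostly background events. This stands, and it favors separate tables.

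**Conclusion.** The point holds for the adverse-event summary tables. If the protocol is followed as written, AEs, SAEs and fatal AEs with onset after the last dose are in no by-arm incidence table, although they are collected through Visit 20. This is a stated rule that gives a poorer result, and not a detail merely left open.

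The untabulated period is 13% of post-randomization AE collection for a completer and more for early stoppers. How many events fall in it, and whether they differ between arms, cannot be derived from the document.

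Two limits apply. Recovery is documented only to day 21 after 14 days of dosing, so it cannot be said that lymphocytes are still recovering throughout the 12 weeks. Nor does the protocol say that the 12-week follow-up exists because immune effects outlast dosing; Section 9.2.6 presents the visits as general risk mitigation.

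The conclusion assumes that the analysis follows Section 9.7.1.8.2 literally. A SAP that is not shown may add a window or a table, in which case the protocol wording should be brought into line.

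**What to change.** Keep the on-treatment TEAE tables as they are. Add by-arm summary tables of AEs, SAEs and AEs leading to death with onset or worsening after the last dose through Visit 20. Amend the restricting sentence in Section 9.7.1.8.2 so that it allows these tables.

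An acceptable alternative is to define the TEAE window as running from first dose through Visit 20, with on-treatment and post-treatment onset shown separately. Separate tables are preferable because they leave the on-treatment percentages unchanged and avoid mixing in background events.

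The cost is one amended sentence and one extra table split. The data are already collected, so no visit or assessment is added.

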9.7.1.8.3 LABORATORY VALUES

Laboratory results will be summarized using International System of Units, as appropriate. For all quantitative parameters listed in [Section 9.5.1.5.3](#), the actual value and the change from baseline to each postbaseline visit and to the end of treatment (defined as the last on-treatment value) will be summarized by visit and treatment group using descriptive statistics. Qualitative parameters listed in [Section 9.5.1.5.3](#) will be summarized using frequencies (number and percentage of subjects), and changes from baseline to each postbaseline visit and to end of treatment will be reported using shift tables. Percentages will be based on the number of subjects with both nonmissing baseline and relevant postbaseline results.

Laboratory test results will be assigned a low/normal/high (LNH) classification according to whether the value was below (L), within (N), or above (H) the laboratory parameter's reference range. Within-treatment comparisons for each laboratory parameter will be based on 3-by-3 tables (shift tables) that compare the baseline LNH classification to the LNH classification at each postbaseline visit and at the end of treatment. Similar shift tables will also compare the baseline LNH classification to the LNH classification for the highest and lowest value during the treatment period.

[Appendix 1](#) (Sponsor's Grading for Laboratory Values) presents the criteria that will be used to identify subjects with treatment-emergent markedly abnormal laboratory values (TEMAVs). Except for phosphate, a TEMAV is defined as a postbaseline value with an increase from baseline to a Grade of 2 or higher. For phosphate, a TEMAV was defined as a postbaseline value with an increase from baseline to a Grade of 3 or higher. When displaying the incidence of TEMAVs, each subject may be counted once in the laboratory parameter high and in the laboratory parameter low categories, as applicable.

Lymphocyte subsets measured (including but not limited to CD4 [T helper cells], CD8 [cytotoxic T cells], CD19 [B cells], CD16/CD56 [natural killer cells] and CD14 [macrophages] and regulatory T cells) will be summarized in the same manner as other

laboratory parameters. Mean lymphocyte subsets and the mean change from baseline in lymphocyte subsets will also be displayed graphically over time by dose.

Serum IgG, IgM, and IgA will be measured and summarized in the same manner as other laboratory parameters.

9.7.1.8.4 VITAL SIGNS

Descriptive statistics for vital signs parameters (ie, systolic and diastolic BP, pulse, respiratory rate, temperature, weight), and changes from baseline will be presented by visit and treatment group.

9.7.1.8.5 ELECTROCARDIOGRAMS

Descriptive statistics for ECG parameters and changes from baseline will be presented by visit and treatment group. Shift tables will present changes from baseline in ECG interpretation (categorized as normal; abnormal, not clinically significant; and abnormal, clinically significant) to the end of treatment.

In addition, the number (percentage) of subjects with at least 1 postbaseline abnormal ECG result in QTcF during the treatment period will be summarized. Clinically abnormal ECG results in QTcF will be categorized as follows:

Absolute QTc interval prolongation:

- QTc interval >450 msec
- QTc interval >480 msec
- QTc interval >500 msec

Change from baseline in QTc interval:

- QTc interval increases from baseline >30 msec
- QTc interval increases from baseline >60 msec

9.7.1.8.6 OTHER SAFETY ANALYSES

Cognitive decline will be assessed as a safety assessment, in addition to efficacy assessments. Cognitive assessments will include the ADAS-cog₁₄, MMSE, CDR, and CBB (Section 9.7.1.6).

9.7.2 Determination of Sample Size

9.7.2.1 Sample Size Rationale in the MCI/Prodromal Cohort

Primary endpoint – derived ADCOMS

The sample size and design characteristics to test the hypothesis for the primary objective based on the primary endpoint, change from baseline of the derived ADCOMS at 18 months, were determined by means of simulations. Extensive study simulations have shown that a total of 500 subjects will be sufficient to demonstrate that the most likely ED₉₀ dose achieves a 25% improvement over placebo with a probability of at least 80% in the interim and final analyses. There is at least a 90% probability of study success for the dose response scenarios where treatment was considered to have a clinically meaningful treatment effect. Simulations have also shown that if there is no obvious dose effect, the probability of falsely claiming superiority to placebo is at most 5%.

For each of the 4 treatment groups (3 active doses and placebo) the final number of subjects per group will differ depending on the observed interim treatment responses. The simulation plan will be an appendix to the statistical analysis plan and will present further details.

vMRI

The null hypothesis is that there is no difference between active dose and placebo. There are 3 null hypotheses corresponding to 3 active doses. The alternative hypothesis is that at least 1 null hypothesis is false (1-sided). The null hypotheses will be tested using Dunnett's method with 1-sided alpha of 0.05. The statistical power was estimated through simulation for a moderate dose-response assumption that the percent reduction in change from baseline of total hippocampal volume compared with placebo would be 15%, 20%, and 25% corresponding to the 3 doses, respectively. The estimated power for the actual planned study sample size is 78% at 18 months assuming an attrition rate of 20% at 18 months. Under a stronger dose-response assumption (ie, the percent reduction in change from baseline of total hippocampal volume compared with placebo is twice as much as that in the moderate dose-response assumption), the estimated power is at least 99% at 18 months.

Amyloid PET

The null and alternative hypotheses and the statistical test are the same as those for vMRI. To estimate the sample size for the amyloid PET imaging subgroup at 18 months, a common SD of the change from baseline was estimated at 0.33 and a reasonable mean difference between treatment and placebo was estimated as 0.25 (standardized uptake value ratio [SUVR]). Assuming a moderate dose-response, the best dose would achieve a difference of 0.25 (SUVR) and the middle and low doses would achieve a difference of 0.2 and 0.15 (SUVR), respectively; this would require a total of 100 subjects from all 4 arms at 18 months to achieve 80% power.

9.7.2.2 Sample Size Rationale for the Mild to Moderate AD Cohort (revised per Amendment 01)

ADCOMS at Month 18

The null hypothesis is that there is no difference between active dose and placebo. There are 2 null hypotheses corresponding to 2 active doses. The alternative hypothesis is that at least 1 null hypothesis is false. The null hypotheses will be tested using Dunnett's test with 2-sided alpha of 0.05 as described for the Mild to Moderate AD cohort in [Section 9.7.1.6.2](#). The statistical power was estimated through simulation for the dose-response assumption that the percent reduction in change from baseline of ADCOMS at 18 months compared with placebo would be 33% and 50% corresponding to the 2 doses, respectively. The estimated power for the actual planned 200 mild to moderate AD subjects is approximately 80% assuming a 2-sided alpha of 0.05. (revised per Amendment 01)

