9.7 Statistical Methods

All statistical analyses will be performed by the sponsor or designee. Statistical analyses will be performed using SAS software or other validated statistical software as required.

All statistical tests will be based on the 5% (2-sided) level of significance, except for the Bayesian methods on the primary endpoint.

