If neither early success nor futility is reached and the study reaches full randomization, all subjects will complete 18 months of treatment. Interim efficacy analyses will be conducted every 3 months after full randomization is reached to assess futility and early success until all subjects complete 18 months of treatment. After full randomization, all study subjects will stop treatment only in the event of futility.

The DSMB will continue to monitor the safety aspects of the study throughout Stage A and Stage B. Details will be provided in the DSMB Charter. The study may be stopped for safety at any time.

The first Bayesian adaptive interim analysis will be conducted when 100 MCI/Prodromal subjects have been randomized into the study (ie, including MCI/Prodromal subjects from Stage A and Stage B). (revised per Amendment 01) Further interim efficacy analyses will be conducted after each additional 50 MCI/Prodromal subjects have been randomized, to a maximum of 500 MCI/Prodromal subjects (ie, at 100, 150, 200, 250, 300, 350, 400, 450, and 500 subjects randomized). If the study reaches full randomization, additional interim analyses will be conducted every 3 months until all subjects complete 18 months of treatment. The study will be monitored for futility at each interim analysis. Starting at the interim analysis for 200 subjects, the study will be monitored for success at each interim analysis. Each interim analysis will be conducted on data for the derived ADCOMS.

In addition, at each interim efficacy analysis, response adaptive randomization will be used to update the allocation of new subjects between placebo and active doses according to a predefined automated algorithm.

The Mild to Moderate AD Cohort (revised per Amendment 01)

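### Section 9.7 sets two-sided 5% for every test except the Bayesian primary analysis, but Section 9.7.2.1 tests and powers vMRI and amyloid PET at one-sided 5%; the stated powers hold only one-sided

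*Protocol*

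**What the plan says.** Protocol Section 9.7 gives the general rule, repeated in the synopsis under Statistical Methods: "All statistical tests will be based on the 5% (2-sided) level of significance, except for the Bayesian methods on the primary endpoint". That is its only exception.

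Section 9.7.2.1 and the synopsis sample size rationale then say that the three vMRI null hypotheses will be tested by Dunnett's "method with 1-sided alpha of 0.05". The alternative is that at least one of the three nulls is false, in one direction. The assumed reductions relative to placebo "would be 15%, 20%, and 25% corresponding to the 3 doses, respectively", and the result is given as: "The estimated power for the actual planned study sample size is 78% at 18 months assuming an attrition rate of 20% at 18 months". With effects twice as large, "the estimated power is at least 99% at 18 months".

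For amyloid PET the same section adopts the hypotheses and test used for vMRI. It assumes an SD of 0.33 SUVR and differences from placebo of 0.25, 0.20 and 0.15, and concludes that "this would require a total of 100 subjects from all 4 arms at 18 months to achieve 80% power".

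Both endpoints have frequentist analyses. vMRI in MCI/Prodromal subjects is a secondary endpoint analysed by MMRM (Section 9.7.1.6.2). PET is an exploratory endpoint analysed by a linear mixed model (Section 9.7.1.6.3). By contrast, Section 9.7.2.2 powers the mild to moderate AD cohort with Dunnett's test at two-sided 0.05, in line with Section 9.7.

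**The concern.** Neither vMRI nor PET falls under the Bayesian exception, so Section 9.7 requires two-sided 5% where Section 9.7.2.1 prescribes one-sided 5%. This is not the common shorthand of one-sided 2.5% for two-sided 5%: one-sided 5% allows twice the error in the tested direction.

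Two things are at stake. First, the same data could be called significant under one section and non-significant under the other, and settling that after unblinding would mean choosing an error rate post hoc. Second, the stated powers belong to a test that the general rule does not allow. For PET this bears on the amount of data collected, because longitudinal scanning stops once at least 25 acceptable 18-month scans per arm and ligand are in hand (Sections 9.2.5.3 and 9.5.1.4.2).

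**Working it through.** **Method.** For dose *i* against placebo, with pooled SD *S* on *N* − 4 degrees of freedom,

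T_i = (mean_i − mean_0) / (S × √(1/n_i + 1/n_0)).

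The one-sided Dunnett test rejects when the largest T_i exceeds its critical value; the two-sided test uses the largest |T_i|. Power is the probability of at least one rejection, following the protocol's alternative. Critical values and power were simulated with 400,000 draws.

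**Amyloid PET: all inputs are in the protocol.** The total is 100 over four arms, so 25 per arm, which agrees with the scanning target. SD is 0.33 and the differences are 0.15, 0.20 and 0.25.

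- Standard error of a difference: 0.33 × √(2/25) = 0.0933.
- Standardised differences: 0.15/0.0933 = 1.61, 0.20/0.0933 = 2.14, 0.25/0.0933 = 2.68.

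| Test | Critical value, 25 per arm | Power at 25 per arm | Power at 30 per arm | Power at 31 per arm |
|---|---|---|---|---|
| Dunnett, one-sided 0.05 | 2.09 | 81.2% | 87.4% | 88.4% |
| Dunnett, two-sided 0.05 | 2.38 | 71.1% | 79.3% | 80.7% |

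The one-sided row reproduces the protocol's 80%; the two-sided row does not. Two-sided, 80% is first reached at 31 per arm, 4 × 31 = 124 subjects.

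**vMRI: calibration only.** The protocol gives percentage reductions but neither the placebo mean change nor its SD, so 78% cannot be checked. The step that can be taken is to accept 78% as correct for the one-sided test, solve for the missing ratio, and then switch to the two-sided test.

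- Subjects: recruitment runs "to a maximum of 500 MCI/Prodromal subjects"; with 20% attrition, 500 × 0.80 = 400, or 100 per arm if the arms were equal.
- Critical values at 100 per arm: about 2.07 one-sided and 2.36 two-sided.
- Ratio of placebo mean change to SD that gives 78% one-sided: 1.435 (SD/mean = 1/1.435 = 0.70).
- Standardised differences: 0.15 × 1.435/√(2/100) = 1.52, and likewise 2.03 and 2.54.

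Group sizes will differ under response-adaptive randomization, so the calibration was repeated for unequal splits of the 400:

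| Completers: placebo/low/middle/high | One-sided (set) | Two-sided | Two-sided, doubled effect |
|---|---|---|---|
| 100/100/100/100 | 78% | 67.4% | 99.9% |
| 140/60/80/120 | 78% | 67.4% | 99.9% |
| 130/50/50/170 | 78% | 67.9% | 99.9% |
| 160/80/80/80 | 78% | 67.1% | 99.9% |
| 150/150/50/50 | 78% | 66.7% | 99.9% |
| 150/50/50/150 | 78% | 67.8% | 99.9% |

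The loss is 10 to 11 points whatever the split, and the claim of at least 99% in the stronger scenario stands.

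**Zone of disagreement.** Statistics between about 2.07 and 2.36 for vMRI (equal arms), or 2.09 and 2.38 for PET, are significant under Section 9.7.2.1 and not under Section 9.7.

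**The case against.** The strongest reply is that nothing has been miscalculated. A reader might infer from the lower figures that 78% and 80% are arithmetic errors. The documents do not support that: Section 9.7.2.1 states its test openly and the PET figure reproduces under it. The specific sentence could also be held to override the general one, in which case both stated powers stand. This part of the reply is sound. The defect is an inconsistency, and the lower figures apply if Section 9.7 governs. But Section 9.7 names its single exception and these endpoints are not in it, so the text cannot stand as written.

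The vMRI 67% is not a recomputation. It assumes that 78% is correct one-sided. If instead the SD/mean of 0.70 is held fixed, two-sided power moves with allocation, from 63% at 150/150/50/50 to 81% at 150/50/50/150. Only the sponsor's simulation can give the figure to print.

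Two stronger readings should be resisted. A reader might infer that vMRI has no multiplicity adjustment, because Section 9.7.1.6.2 does not name Dunnett for the MCI/Prodromal cohort; Section 9.7.2.1 does name it. A reader might also infer that the trial's main evidence of disease modification is underpowered. Section 9.2.5.4 gives vMRI a supporting role, PET is exploratory, and success and futility rest on the Bayesian ADCOMS analysis.

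Finally, the PET 71% is for exactly 25 per arm analysed together. The scanning target applies per ligand, so more than one ligand could yield more scans, if results can be pooled at the same SD.

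**Conclusion.** The concern holds as an internal contradiction with a measurable consequence for two stated powers. Sections 9.7 and 9.7.2.1 fix different tests for one secondary and one exploratory endpoint, and an analysis plan could follow only one of them.

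- **PET:** firm, from stated inputs. Two-sided power is about 71% at 100 subjects against the stated 80%; about 124 subjects are needed for 80%. This assumes equal arms of 25 and power defined as at least one rejection.
- **vMRI:** conditional. If 78% is right one-sided, two-sided power is about 67% (66% to 68% over the allocations tried). The stronger scenario keeps its stated 99% or more.

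The primary analysis, the 500-subject maximum and the success and futility rules are untouched.

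**What to change.** Keep the two-sided 5% rule in Section 9.7. In the vMRI and amyloid PET parts of Section 9.7.2.1, and in the matching synopsis text, replace the one-sided test and alternative by two-sided Dunnett at 0.05, as Section 9.7.2.2 already does for the mild to moderate AD cohort. Restate PET power as about 71% at 100 subjects. Restate vMRI power from a re-run of the sponsor's own simulation, expected at about 67%, and give the placebo mean change, SD and allocation behind it.

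If one-sided testing is really intended, list vMRI and PET as explicit exceptions in Section 9.7 and in the synopsis; the stated powers can then stay.

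The cost is text plus one simulation run, and two less favourable powers. Only if 80% for PET is to be kept two-sided does the data requirement change: 24 more subjects with an 18-month scan, and a scanning target of about 31 rather than 25 per arm.
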